The design size contemplates enrolling up to one hundred and twenty (120) subjects who will successfully follow through to completion of their participation in at least the first treatment portion of the study (first 3-month treatment period). The subjects will be randomly assigned to: twice-per-day active, once-per-day active or twice-per-day placebo in a 1:1:1 ratio.

The results of the first migraine RCT did not show evidence of stratification based on gender or clinical site or baseline headache frequency. Envelopes containing

randomization assignments will be grouped in batches of six, each batch containing two of each of the three assignment arms. The batches of envelopes will be randomly shuffled by an agent not involved with the study. A given batch will be completed before the next batch is opened. This procedure results in 20 possible different arrangements, for six subjects, of the ordering of treatment and placebo assignments. The unblinded coordinator will record the subject's designation but will not share the assignment with the subject, principal investigator, or statistician. Each study site will be individually randomized (no central randomization).

The assessment of the primary endpoint will be completed by a blinded, central statistician. The subjects will be told, within the informed consent document, of the existence of a placebo arm. Subjects will be told that the device stimulates the brain stem. Subjects will be told that they will receive at least 3-months of active treatment during the 6-month treatment period. In fact, subjects in the placebo arm in the first 3-month period will be switched to active in the second 3-month period. Subjects will be asked to guess (and provide reasons) about their treatment assignment at the end of the first 3-month treatment period and at the end of the second 3-month treatment period. Subjects will also be asked, after their very first treatment in the clinic, a series of questions designed to assess the quality of blinding (to provide evidence that the placebo device is an effective sham).

4) Study Schedule; Subject Enrollment and Activities

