- To assess whether BID active treatment provides therapeutic gains over QD active treatment, the reductions in migraine headaches, the reduction in the number of acute (prescribed) medication taken, the reduction in subject-perceived headache pain scores, the normalized percent-change in monthly headache days, and the 50% responder rates in the BID active-treatment subjects and QD active-treatment subjects during the following periods will be compared: the first treatment month, the third treatment month, the sixth treatment month and the final month of the post-treatment period. Additionally, change scores for the QOL measures (HIT-6, BDI, BAI and the Pittsburgh Sleep Quality Assessment) at the end of the first and second treatment periods and the post-treatment observation period will also be assessed. The response kinetics for each of these parameters will be evaluated by comparing time courses for each of the three treatment arms. All change scores will be calculated relative to baseline measures.
- To assess whether six months of active treatment provides improved levels of migraine prevention relative to three months of active treatment, comparisons of the reductions in migraine headache days, the reduction in the number of acute (prescribed) medication taken, the reduction in subject-perceived headache pain scores, the normalized percent-change in monthly headache days, and the 50% responder rates during the third treatment month and the sixth treatment month (relative to baseline) for the QD active and the BID active groups will be performed. Change scores for the QOL measures (HIT-6, BDI, BAI and the Pittsburgh Sleep Quality Assessment) for the QD active and the BID active groups at the end of the first and second treatment periods (relative to baseline) will also be compared. Additionally, these measures will also be compared between the BID active and BID placebo groups during the sixth treatment month. All change scores will be calculated relative to baseline measures.

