An experienced, independent and blinded Statistician will analyze and summarize the daily headache diaries for all subjects and evaluate the primary endpoint and observational aims. A blinded reviewer will analyze and summarize the quality of life data.

The primary aim of this trial is to determine if subjects randomized to the twice-daily active group, have a greater reduction in the number of headache days than those assigned to the twice-daily placebo group. For this study, the reduction in headache days (primary endpoint) is calculated as the number of headache days during the baseline month minus the number of headache days during treatment month three. An intent-to-treat methodology will be employed for the primary aim; however, per protocol analyses will also be conducted for comparison. Analysis of the primary endpoint and the secondary headache-related endpoints assessed in the daily diary will be performed for all subjects that complete at least 25 diary entries or more during the relevant 28-day treatment month. Treatment compliance is defined as completion of at least 50% during

each treatment months (for the per protocol evaluation). Subjects with treatment compliance below 50% during any treatment month will be assigned to the intent-to-treat group only. As accurate assessment of some of the secondary endpoints assessed during study period do not depend on daily headache diary compliance, treatment compliance will be the only criteria for inclusion in the per protocol analysis of those secondary outcomes. Statistical significance will be defined with a Type I error of 5% ($\alpha=0.05$). Wilcoxon rank-sum tests (for non-normal data) or a paired student's t-tests (for normal data) will be used to establish whether the reductions in headache days between the baseline and third treatment month in each treatment arm are statistically significant. Mann-Whitney U tests (for non-normal data) or unpaired student's t-tests (for normal data) will be used to determine whether the reduction in migraine headaches in the twice daily active treatment arm subjects is significantly greater than that observed in the twice daily placebo treatment arm subjects. No interim analyses of efficacy are planned.

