The study is powered for the primary aim. Given a sample size of 40 subjects per arm and a standard deviation in the reduction of headache days of $\sigma=3.36$, a mean difference for the reduction in the number of headache days between the twice-daily active arm and the twice daily placebo arm of 2.13 days will be detectable at the 95% significance level ($\alpha=0.05$) with 80% power. The figure below shows the sensitivity of the detectable differences relative to the value of the standard deviation and the sample size.

The study is intentionally overpowered for the primary endpoint (based on the mean reduction of 2.73 headache days in the first RCT), however, a sample size of 40 subjects per arm should allow for sufficient power to assess the majority of secondary endpoints at

the end of the sixth treatment month and at the end of the post-treatment observation period given the expected dropout rate of 5 subjects per group during each 3 month period. Notably, while the 50% responder rate (a secondary outcome) will be evaluated as a discrete variable, it is unlikely to yield statistical significance due to insufficient sampling. Therefore, the similar measure of percent-change in migraine days will also be compared as a continuous variable across groups.

An analysis will be conducted to determine if blinding was successful using descriptive statistics.

9) Quality Assurance Monitor

A quality assurance monitor will be used to audit study sites. Following written procedures, the monitor will verify that the clinical trial is conducted and data are generated, documented and reported in compliance with the protocol, GCP and applicable regulatory requirements. Investigational site(s) will provide direct access to all trial related sites, source data/documents and reports for the purpose of monitoring and auditing by the sponsor and inspection by regulatory authorities.

10) Procedures for adverse events:

- **Documentation and assessment**
 - Following the informed consent process, clinical study subjects will be routinely questioned about adverse events at study visits and telephone contacts by the clinical research sites. All adverse events, regardless of treatment group, or suspected causal relationship to the investigational device, will be recorded in the subjects' case report forms in their study binder.

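### Section 8 gives no multiplicity rule for 49 between-arm secondary comparisons, and none of the 32 once- versus twice-daily comparisons is named as the test of aim 3

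*Combined protocol and SAP*

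**What the plan says.** Section 8 states the significance level once, for the analysis as a whole: "Statistical significance will be defined with a Type I error of 5" percent. It names tests only for the reductions in headache and migraine days (within arm, and BID active against BID placebo). It gives no adjustment, no order of testing and no key secondary endpoint, and it does not call the secondary endpoints exploratory or descriptive.

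On size, section 8 says "The study is powered for the primary aim". It also argues that 40 per arm leaves enough power for most secondary endpoints at later times, and it comments on whether the 50% responder rate will reach significance. Section 3 randomizes to "twice-per-day active, once-per-day active or twice-per-day placebo in a 1:1:1 ratio".

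Once- versus twice-daily treatment is the third numbered aim in the Background. Section 7 addresses it with five diary measures, each at "the first treatment month, the third treatment month, the sixth treatment month and the final month of the post-treatment period", and with four questionnaires at three visits. No measure or month is singled out.

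**The concern.** A single primary endpoint protects the main claim, but nothing limits what follows it. The plan treats secondary results as candidates for significance without saying which of them may carry a claim.

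Aim 3 is the most exposed. Equal benefit from one and two daily treatments is a realistic outcome. With 32 comparisons and no main test, one nominally significant difference could be presented as the answer, and its error rate would be well above 5%.

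The 9 month-6 comparisons of BID active with the former placebo arm are also open to chance findings, because by then both arms receive BID active treatment. In addition, the first treatment period is analyzed while later periods are still running. Early results could therefore shape which later comparison is emphasized.

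**Working it through.** **1. The plan's own figure.** Inputs from section 8: "Given a sample size of 40 subjects per arm", SD 3.36, 80% power, and a difference from "the twice daily placebo arm of 2.13 days will be detectable at the 95% significance level". Two-sided testing is assumed, since the plan does not say.

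n per arm = 2(1.960 + 0.842)² × 3.36² / 2.13² = 39.1, which rounds up to 40. Power at 40 per arm is 80.9% by the normal formula and 80.0% by the t distribution. The stated design reproduces.

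**2. Count of pairwise between-arm secondary comparisons (section 7).**

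- BID active vs placebo, month 3: percent change and responder rate (2), acute medication (1), pain score (1), HIT-6 (1), BDI and BAI (2), sleep (1) = 8.
- BID vs QD: 5 diary measures × 4 periods = 20, plus 4 questionnaires × 3 visits = 12; total 32.
- BID active vs placebo arm, month 6: 5 diary measures + 4 questionnaires = 9.
- Total: 8 + 32 + 9 = 49.

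This leaves out the three-arm BMI, BDI, BAI and time-course comparisons, and the per-protocol repeats.

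**3. Expected number of false positives if every null is true.** This is 0.05 × k, whatever the correlation: 0.05 × 49 = 2.45 and 0.05 × 32 = 1.6.

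**4. Chance of at least one, if independent.** 1 − 0.95^k:

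- 8 month-3 BID-placebo comparisons: 34%
- 32 BID-QD comparisons: 81%
- all 49: 92%

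**5. Chance of at least one, with correlation.** The documents give no correlations, so these are assumed. For the 32 BID-QD comparisons, null test statistics were simulated (100,000 draws per setting) with a constant correlation between measures and between times:

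| Between measures | Between times | All 9 measures correlated | Diary and questionnaire blocks independent |
|---|---|---|---|
| 0.5 | 0.5 | 61% | 67% |
| 0.5 | 0.8 | 50% | 55% |
| 0.8 | 0.5 | 43% | 53% |
| 0.8 | 0.8 | 32% | 42% |

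That is roughly 30-70%.

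For the 49, the simulation used 200,000 draws per setting and a shared BID arm. Correlations ran from weak (0.3 between diary measures, 0.3 between questionnaires, 0.2 across the two, 0.3 between times) to very strong (0.8, 0.6, 0.5, 0.7). The chance falls from 87% to 62% over that range. In the same settings the figure for the 32 falls from 75% to 46%.

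**6. What one named BID-QD test could detect.** Difference = 3.36 × √(2/n) × (1.960 + 0.842). This gives 2.10 days at 40 per arm, 2.25 at 35 and 2.43 at 30. The last two sizes correspond to "the expected dropout rate of 5 subjects per group during each 3 month period". Using SD 3.36, which the plan gives for headache days in the primary comparison, is an assumption here.

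**7. Why not Bonferroni.** Over 49 tests the level is 0.05/49 = 0.00102. At 40 per arm, power for 2.13 days drops to 33%.

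**The case against.** The strongest reply is that the 5% sentence is general. The tests named with it cover only headache and migraine days, the study is powered for the primary aim, and no threshold is attached to each secondary endpoint. The secondaries might have been meant descriptively. This partly stands: applying 5% to each of them is an inference. But section 8 also discusses power and significance for secondary endpoints, so the intent is at best unsettled, and one sentence would settle it.

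A second reply is that the aim-3 question is directional (does BID add benefit over QD?), and its measures and months are listed in advance. This also has weight. A chance result favoring BID occurs in about 16-33% of the simulated trials when all nine measures are correlated, about half the two-sided figure. That is still above 5%. In addition, section 7 says the 12 BID-QD questionnaire items will be assessed, so counting each as a formal test is a reading. The 20 diary comparisons alone give 64% if independent and 27-48% at equal correlations of 0.8 to 0.5.

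A reader might go further and infer that chance secondary findings are close to certain, for instance by counting every comparison in section 7. That count is 49 + 18 + 54 + 24 + 9 + 5 = 159 (adding, in order, month 3 vs 6, durability diary, durability questionnaires, BMI/BDI/BAI, and correlation and model analyses). It is 186 if 18 further durability results and about 9 time courses are also tested. The documents do not support the inference. At least 96 of these (18 + 54 + 24) are within-arm comparisons, and many are against baseline. Placebo response or regression to the mean could make those nulls false, so significance there need not be a chance finding. Near-certainty also requires independence, which cannot hold for measures taken on the same patients, from the same diary counts, at repeated times.

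**Conclusion.** The concern holds at moderate size. There are 49 pairwise between-arm secondary comparisons with no multiplicity rule and no order, and 32 of them bear on a numbered aim that has no main test. The expected counts of 2.45 and 1.6 rest only on all nulls being true and on each comparison being judged at 5%. The chances of at least one false positive (roughly 30-70% for the 32, roughly 60-87% for the 49) rest also on assumed correlations; 81% and 92% are the values under independence.

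A reader might infer that the plan will more often than not yield a false BID-QD difference. Over the assumed range the chance lies on both sides of one half, so that is not established. Nor is the primary result in doubt: one endpoint, one main between-arm comparison and no interim efficacy analysis leave its 5% intact. What is established is that the error rate for aim 3, and for secondary claims in general, is uncontrolled and well above 5% over every setting examined.

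**What to change.** Add to section 8:

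1. Name one BID-QD comparison as the test of aim 3: change in migraine headache days at treatment month 3.
2. If the primary test is significant, test in fixed order at two-sided 5%, stopping at the first failure: percent change in migraine days (BID active vs placebo), then the named BID-QD test, then the other month-3 BID-placebo secondaries in a prespecified order. Put the 50% responder rate last. Section 8 expects it to miss significance for lack of sample, so anywhere earlier it would probably block what follows.
3. Alternatively, test the named BID-QD comparison at 5% as a stand-alone question, so that it does not depend on the BID-placebo sequence. Aim 3 then has its own 5%, but the combined error of that test and the BID-placebo sequence is bounded by 5% + 5% = 10% rather than 5%. The plan should say so.
4. Report all other secondary comparisons as estimates with 95% confidence intervals and no significance claim.

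This changes wording only. Sample size, data collection and the primary test stay as they are. The downside is that fewer secondary endpoints can be called significant. Under option 2, a failure on percent change would also leave aim 3 without a formal test.

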SCION NEUROSTIM, LLC:

Title: A Non-Invasive Neuromodulation Device for Prevention of Episodic Migraine Headache

Background

This study is a multi-center, triple-blinded, placebo-controlled, randomized clinical trial for adjunctive prophylactic treatment of episodic migraine headache (with or without aura) using a caloric vestibular stimulation (CVS) device developed by Scion NeuroStim, LLC (SNS). The investigational use of the CVS device for episodic migraine headache has been reviewed by the FDA and is classified as NSR (non-significant risk).

Efficacy of neuromodulation therapy for migraines is reasonably well-established. Traditionally, however, neuromodulation, especially when accomplished through an expensive, surgically implanted device, has been available only as a treatment of last resort, to be used (and covered by health insurance) if, but only after, patients have failed all other interventions, principally pharmaceuticals. Typically, patients receive neuromodulation for migraines only after they are refractory or close to being refractory. SNS envisions changing that paradigm, providing effective early interventions and thereby improving outcomes for migraine patients. The CVS device is non-invasive and utilizes the same underlying mode of neural modulation (activation of the vestibular nuclei in the brainstem) that for a century has been well-understood by the medical profession and has been used safely via caloric irrigators for diagnostic purposes, for example in ENT practices to assess balance and in the ED to assess brain function. The device is easy to operate; it can be used safely at home by a patient under the supervision of a prescribing physician. Through availability and use of the CVS device, prophylactic neuromodulation therapy for migraines can become an inexpensive and early, rather than an expensive and belated, therapeutic option.

A pivotal RCT study of episodic migraine headache using the device has been completed (NCT01899040). The primary endpoint was met. Active arm subjects showed immediate and steady declines in migraine days over the treatment period and exhibited significantly fewer migraines during the third treatment month (-3.6 ± 0.7 days, $-46.1\% \pm 7.3\%$), than placebo arm subjects (-0.9 ± 0.7 days, $13.5\% \pm -14.1\%$, $p = 0.014$). The study described herein is designed to further the evaluation of CVS neuromodulation, addressing the following aims:

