Less likely:

- Nausea/vomiting

- Headache
- Coughing

All of these side effects are expected to resolve once use of the device is stopped.

7) Study Endpoints

- **Primary Efficacy Endpoint for the Study**

For the twice-per-day active-treatment subjects: During the third month of the first treatment period, their average total number of monthly migraine headache days will be lower than their comparable averages derived from the pre-treatment baseline period. Also, this reduction in migraine headache days will exceed that observed in the twice-per-day placebo group.

- **Secondary Endpoints:**

- The normalized percent-reduction in migraine headache days (during the third treatment month relative to the pre-treatment baseline) in the BID active-treatment subjects will be compared to that of the BID placebo-treatment subjects. Groups will be compared on the basis of percent-change (continuous variable) as well as the “50% responder rates” (discrete variable).
- The reduction in acute (prescribed) medication taken (during the third treatment month relative to the pre-treatment baseline) in the BID active-treatment subjects will be compared to that of the BID placebo-treatment subjects.
- The reduction in subject-perceived headache pain scores (during the third treatment month relative to the pre-treatment baseline) in the BID active-treatment subjects will be compared to that of the BID placebo-treatment subjects.
- To assess whether active treatment results in improved quality of life (related to the reduction in migraine), HIT-6 change scores (end of the first treatment period versus baseline) will be compared across BID active-treatment subjects and BID placebo-treatment subjects.
- To assess whether active treatment results in improvements in depression or anxiety, BDI and BAI scores (end of the first treatment period versus baseline) will be compared across BID active-treatment subjects and BID placebo-treatment subjects.
- To assess whether active treatment results in improved sleep quality, Pittsburgh Sleep Quality Assessment change scores (end of the first treatment period versus baseline) will be compared across BID active-treatment subjects and BID placebo-treatment subjects. Correlational analysis will be performed to determine whether a relationship exists between improved sleep and reduced migraine frequency.

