- To assess whether CVS therapy provides durable migraine prevention after therapy has ceased, the number of migraine days, the reduction in subject-perceived headache pain scores, the number of acute (prescribed) medication taken, during each month in the post-Tx observation period will be compared to both baseline and the final treatment month in all 3 treatment groups. The normalized percent-change in monthly headache days and the 50% responder rates (relative to baseline) will also be assessed. Additionally, the QOL measurements (HIT-6, BDI, BAI and Pittsburgh Sleep Quality Assessment scores) at the final visit will be compared to both the baseline and the 6 month scores.
- Measures of body mass index for each subject will be calculated at baseline, after three and six months of treatment and after the post-treatment observation period and compared across the three treatment

arms.

- Measures of depression (Beck Depression Inventory) and anxiety (Beck Anxiety Inventory) for each subject will be calculated at baseline, after three and six months of treatment and after the post-treatment observation period and compared across the three treatment arms.
- To assess whether the reduction in migraine days relates to the number of active CVS treatments performed, correlational analyses will be performed to assess whether the change in the total number of headache days during defined study periods (first treatment period, second treatment period and post-treatment observational period) is a function of the cumulative CVS treatments performed. Additionally, approaches such as the GLIMMIX procedure for generalized linear mixed models will also be performed to determine the probability of a headache on any given day is predicted by the cumulative number of active treatments performed.

As noted above, the baseline period and the first 3-month treatment period will constitute a complete RCT. Those data will be analyzed when the targeted number of subjects (120) complete the first treatment period. Subjects will continue on to the second 3-month treatment period without interruption, as they progress through the study period. For additional clarity, the stated primary endpoint will be evaluated for the baseline period + first 3-month treatment period.

[figure not shown]
8) Statistical Analysis and Study Size

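### The within-arm test for non-normal data is named as the unpaired Wilcoxon rank-sum; it should be the paired Wilcoxon signed-rank (minor)

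*Combined protocol and SAP*

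**What the plan says.** Section 8 (Statistical Analysis and Study Size) defines the reduction as each subject's baseline-month count minus the month-3 count. To judge whether the "reductions in headache days between the baseline and third treatment month in each treatment arm are statistically significant", it gives two options: "Wilcoxon rank-sum tests (for non-normal data) or a paired" Student's t-test when the data are normal. The next sentence turns to twice-daily active versus twice-daily placebo and names "Mann-Whitney U tests (for non-normal data) or unpaired" Student's t-tests.

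Section 7 (Study Endpoints) states the primary efficacy endpoint in two parts for the twice-daily active arm. The first is that in month 3 "their average total number of monthly migraine headache days will be lower than their comparable averages derived from the pre-treatment baseline period". The second is that this reduction exceeds the one in the twice-daily placebo arm.

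No section names a signed-rank test, and none says how normality will be judged.

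**The concern.** The within-arm question is a paired one, and the option for normal data in the same sentence is a paired test. The option for non-normal data is not. Wilcoxon rank-sum and Mann-Whitney U are two names for one independent-samples test, so the plan assigns the same unpaired test to a paired question and, one sentence later, to an unpaired one.

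The sentence also cannot be carried out as written. The reductions in one arm form a single sample, and a rank-sum test needs two. An analyst must either depart from the plan or set the baseline counts against the month-3 counts as if they came from different people. The second course discards the pairing and miscalibrates the p-value for the first part of the primary endpoint, and for the same test in the other arms. Because the plan gives no rule for judging normality, nobody can say in advance whether this branch will be used. A correction made after the data are seen would be post hoc.

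**Working it through.** **The plan's own figure.** Inputs from section 8: 40 per arm, SD of change 3.36 days, alpha 0.05, power 80%. Sidedness is not stated; two-sided is used here. The normal approximation gives (1.960 + 0.842) × 3.36 × √(2/40) = 2.10 days. The two-sample t calculation gives 2.131 days, and power of 0.7995 at 2.13 days. The stated 2.13 days is reproduced. It concerns the between-arm test only.

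**Direction of the error.** Let ρ be the correlation between a subject's baseline and month-3 counts, with equal SD s in both months. An unpaired test takes the variance of the difference in means as 2s²/n, but the true value is 2s²(1−ρ)/n. Under the null, its test statistic therefore has SD of about √(1−ρ) rather than 1, and the real type I error is about 2[1 − Φ(1.96/√(1−ρ))]:

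- ρ = −0.3: 1.96/1.140 = 1.719, giving 8.6%
- ρ = 0: 5.0%
- ρ = 0.3: 1.96/0.837 = 2.343, giving 1.9%
- ρ = 0.5: 1.96/0.707 = 2.772, giving 0.6%

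**Simulation.** There were 20,000 runs per setting with one arm of 40. Counts were normal and rounded to whole days, with baseline mean 8 (assumed) and two-sided 0.05. The SD of change was held at 3.36, so s = 3.36/√(2(1−ρ)). The documents do not give ρ, so a range is shown. Entries are rejection rates, rank-sum / signed-rank, by true reduction.

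| ρ | s (days) | 0 days | 0.9 days | 1.5 days | 2.13 days | 3.6 days |
|---|---|---|---|---|---|---|
| −0.3 | 2.08 | 0.084 / 0.050 | 0.46 / 0.36 | 0.84 / 0.77 | 0.98 / 0.97 | 1.00 / 1.00 |
| 0 | 2.38 | 0.048 / 0.049 | 0.37 / 0.36 | 0.77 / 0.77 | 0.97 / 0.97 | 1.00 / 1.00 |
| 0.3 | 2.84 | 0.021 / 0.048 | 0.24 / 0.36 | 0.64 / 0.77 | 0.93 / 0.97 | 1.00 / 1.00 |
| 0.5 | 3.36 | 0.007 / 0.048 | 0.13 / 0.36 | 0.47 / 0.77 | 0.85 / 0.97 | 1.00 / 1.00 |
| 0.7 | 4.34 | 0.001 / 0.050 | 0.04 / 0.36 | 0.22 / 0.76 | 0.61 / 0.97 | 1.00 / 1.00 |

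The 3.6-day and 0.9-day columns are the active and placebo changes that the Background reports from the earlier trial. The 1.5-day column is illustrative.

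**Effect on the primary endpoint.** Take success to mean that the within-arm test in the twice-daily active arm and the between-arm Mann-Whitney test are both significant (4,000 runs per setting):

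- True changes 3.6 and 0.9 days: 0.934 under either within-arm test at ρ = 0.3; 0.9337 with rank-sum and 0.9353 with signed-rank at ρ = 0.7, a gap of 0.16 percentage points.
- True changes 3.03 and 0.9 days (0.9 + 2.13 = 3.03): 0.7835 under either test at ρ = 0.3; 0.7648 and 0.7652 at ρ = 0.5; 0.768 and 0.776 at ρ = 0.7, a gap of 0.8 points.

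**The case against.** The strongest reply is that this is a slip of terminology. The variable is defined as one difference per subject, a paired t-test stands in the same sentence, and an experienced statistician would run the signed-rank test without hesitation. On that reading no result is ever affected. This is probably what was meant. It is still not what the plan says, and a pre-specified test should not depend on the reader's guess.

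Second, the table uses normal data, for which the plan would choose the paired t-test. The table does illustrate direction more than exact size. However, simulations with skewed counts and a baseline confined to 4–14 days also gave a conservative rank-sum test, with type I error of about 0.5–1% against 5% for signed-rank.

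Third, the rows with high correlation need more spread than the entry criteria readily allow. A flat distribution over 4–14 days has SD √((11² − 1)/12) = 3.16. With equal SDs this gives ρ = 1 − 3.36²/(2 × 3.16²) = 0.44, so the rows at 0.5 and 0.7 are extreme if the SDs are equal. Unequal SDs give the same direction: 2.5 and 3.5 days imply ρ = 0.41, a rank-sum type I error of 1.5%, and power of 90% against 97% for a 2.13-day reduction.

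Fourth, no section says that both parts of the endpoint must reach p < 0.05, and section 8 frames and powers the primary aim as the between-arm comparison alone. That is so. The joint-success rule is an assumption made here to size the effect, and the effect it shows is small.

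**Conclusion.** The test named for the non-normal branch is the wrong one, and nothing elsewhere in the document corrects it. The error is minor. It touches only that branch; the paired t-test, the between-arm tests and the 2.13-day, 80% power statement all stand.

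If the rank-sum test were run literally, it would be conservative provided baseline and month-3 counts are positively correlated. That is usual for repeated counts in one person, but the documents do not state it. With negative correlation the test would reject too often. The loss of power falls on small within-arm changes. At the 3.6-day active-arm change of the earlier trial, both tests have power close to 1. At its 0.9-day placebo change with ρ = 0.5, power is 13% against 36%. A literal reading could therefore sharpen a contrast of significant in active, not significant in placebo, which is not evidence of a treatment difference in any case.

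**What to change.** In section 8, change rank-sum to signed-rank in the sentence on the within-arm change from baseline to month 3, and keep Mann-Whitney U for comparisons between arms. The cost is one word, made before the data are analysed, with no effect on sample size, data collection or the between-arm analysis.

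Optionally, add one sentence saying that the other within-subject comparisons in section 7 also use paired tests. These are month 3 against month 6, and the post-treatment months, which "will be compared to both baseline and the final treatment month in all 3 treatment groups". Section 7 names no test for them, so the wrong name could carry over.
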